Pharmacist Management of Attention Deficit Hyperactivity Disorder
Medication Refill Requests

Study Protocol and Statistical Analysis Plan

[name], MPH, [name], [name], PharmD, E. [name], [name], MA, [name], BA, [name], MS, [name], [name], [name]

From The Permanente Medical Group (Division of Research, Virtual Care Team, Adult and Family Medicine regional leads, and TPMG Consulting Services) and Pharmacy Services, Kaiser Permanente Northern California, all in Oakland, CA

Version date: August 27, 2024

NCT06388694

Abstract

Importance. Enhancing the management of messages from patients and providing high-quality, consistent care are top priorities for The Permanente Medical Group (TPMG) and Kaiser Foundation Hospitals/Health Plan (KFH/P). A special extension of the Ryan Haight Act currently enables providers to prescribe controlled substances via telehealth interactions but expires in December 2024. Information about the quality of care provided via telehealth prescribing of controlled substances by pharmacists and primary care physicians would be helpful to inform care delivery within Kaiser Permanente and beyond.

Objective. To compare pharmacist management of refill authorization requests for attention deficit hyperactivity disorder (ADHD) medications with physician management regarding quality of care, efficiency of service, and parent satisfaction.

Design, setting, and participants. This cluster randomized clinical trial will include parents of children in Kaiser Permanente Northern California who request ADHD medication refills via secure messages from April 29 to June 28, 2024. Of KPNC's 63 facilities eligible for inclusion, we will assign 32 to Pharmacist Care and 31 to PCP Care.

Intervention. In the intervention group, a regional team of pharmacists will manage electronic refill authorization requests for ADHD medications using a standard protocol. In the comparison group, pediatricians will manage these visits using a similar protocol.

Main Outcomes and Measures. The primary outcome is whether a patient who did not have a weight recorded in the 6 months before the refill request was referred for a primary care follow-up visit. Secondary outcomes are the days from the secure message request to the prescription order and medication fill, and parent satisfaction.

Potential Results. We will test the hypotheses that Pharmacist Care compared with PCP Care will have higher quality of care, faster time to prescriptions and fills, and higher parent satisfaction.

Potential Conclusions and Relevance. If pharmacist care for ADHD medication refill requests has better or similar outcomes compared with PCP care, this will provide evidence supporting continuation of this approach. This study's findings will be useful for KPNC and to inform discussions about renewing the special extension of the Ryan Haight Act that allows this approach.

1. Specific Aims and Hypotheses

Enhancing message management and virtual urgent care options for patients are among TPMG and KFH's top priorities. As team-based inbox management is further developed, evaluating its clinical effectiveness and outcomes in terms of patient care experience and costs will provide valuable information for operational planning. In addition, sharing what we learn with other health care systems through talks and publications will help highlight TPMG's reputation as a group that innovates to support clinicians while increasing patient access through virtual care.

This study will compare the clinical outcomes and costs of two alternative modes of management of parent requests for refills of medications for attention deficit hyperactivity disorder (ADHD): management by a regional team of pharmacists, vs. management by primary care physicians. Patients will be included if they are younger than 18 years and if their parent's

secure message request was sent to a pediatrician or family medicine physician (but not to a psychiatrist). We will conduct a cluster randomized trial in 63 facilities in Kaiser Permanente Northern California to compare Pharmacist Care with Physician Care for patients with ADHD medication refill requests with regard to:

Aim 1. Quality of care

Example hypothesis: Patients without a weight recorded in the past 6 months will be more likely to receive referral for a follow-up weight check in the Pharmacist Care group than the Physician Care group.

Aim 2. Timeliness of care

Example hypothesis: Patients managed via Pharmacist Care will have a faster time to refill prescription than those managed via Physician Care.

Aim 3. Parent satisfaction

Example hypothesis: Parents in the Pharmacist Care group will report comparable satisfaction with the process compared with the Physician Care group.

2. Background and Significance

During the COVID-19 pandemic, the federal Drug Enforcement Agency (DEA) and Health and Human Services (HHS) created a temporary special flexibility (under the Ryan Haight Act) to allow clinicians to prescribe refills of controlled substances via telemedicine interactions. Prior to this, patients needing refills of controlled substances, including medications for attention deficit hyperactivity disorder (ADHD), had to make in-person doctor's office visits for refill requests.

Thanks to this special flexibility, Kaiser Permanente Northern California has been able to offer patients and parents the option of requesting medication refills via secure messages and structured refill authorization requests sent via the electronic health record (EHR) portal. To assist busy primary care physicians (PCPs) who would receive these requests in their inboxes, pharmacists have taken charge of replying to refill requests for all adults aged 18 years and older. Starting in April 2024, the regional pharmacist team will also start to take charge of replying to refill requests sent to pediatricians and family medicine physicians for children and adolescents younger than 18 years starting in April 2024.

The special flexibility granted by the DEA and HHS to allow refills of controlled substances via telemedicine is set to expire on December 31, 2024 if not renewed. The current study will evaluate the effectiveness of providing pharmacist care for ADHD medication refill authorization requests for children and adolescents. It will generate information that helps KPNC enhance our quality of care, and will also contribute to broader national evidence on the effectiveness of virtual care approaches for such needs.

Appropriate management of ADHD medication refills is a quality measure in the Healthcare Effectiveness Data Information Set specified by the National Committee for Quality Assurance. Specifically, the HEDIS measure specifies that children between 6 and 12 years of age who have had a prescription for ADHD medication and have remained on the medication for at least 210 should have at least 2 follow-up visits with a practitioner in 9 months. A key purpose of such

follow-up visits is to check the child's weight to ensure that their weight gain is not falling behind associated with ADHD medication use.

3. Innovation

Pharmacist management of secure messages from patients is innovative in not having been adopted or evaluated at large scale. Preliminary anecdotal and unpublished information from within TPMG suggests that pharmacists' scope of practice is well-suited to message management for many specific conditions based on treatment algorithms. At our KP San Francisco medical center, pharmacists have been able to take charge of messages for a range of issues, including refill authorization requests and requests to manage chronic conditions (hypertension, osteoporosis, attention deficit disorder, gout) and time-limited conditions (sexually transmitted infections, latent tuberculosis, opioid tapering, and assessment of Paxlovid eligibility).

4. Approach

4.1. Design, setting, and participants.

This cluster randomized clinical trial will assign parent secure message requests to pediatricians or family medicine physicians for ADHD medication refills for children aged <18 years to either Pharmacist Care or Physician Care. The unit of randomization is the KPNC facility. KPNC is an integrated health care system with 4.5 million members served by more than 9700 physicians and 90,000 employees in 21 hospitals and 207 medical offices. It has a mature EHR (EPIC/HealthConnect, adopted circa 2008) and encourages members to use a wide array of options for outpatient care, including secure messages to physicians via the EHR portal, e-visits, video, telephone, and in-person office visits.

The target population is children and adolescents aged <18 years whose parents send a refill authorization request (RAR) for an ADHD medication to their child's pediatrician. An RAR is a highly structured electronic communication that does not allow the requestor to add any free text. This structure makes it possible for either a pharmacist or physician to handle the RAR.

The regional pharmacy team started to handle free-text secure message requests for refills from parents of patients with PCPs in pediatrics during a pilot period starting April 11, 2024. Secure messages are different from RARs because they contain free text. These were found to be difficult to flag and send to the regional pharmacy team because accurately identifying the relevant secure messages required manual handling. The rate of such messages that could be identified per day would not have reached the intended sample size for this study. Thus, this study was designed to focus only on RARs, which are much simpler to identify consistently. The regional desktop medicine leader sent an email to the pediatric department at every facility to ask that during the study period, they ignore RARs from facilities randomized to Pharmacist Care, but continue to handle RARs from facilities randomized to Physician Care.

The formal study period will include patients with secure messages sent to the regional pharmacy team from May 6, 2024 to June 21, 2024 (7 weeks). The unit of analysis will be the RAR, allowing some patients to appear up to two times in the study cohort.

4.2. Intervention.

All procedures will be conducted as part of standard of care. In the Pharmacist Care group, each RAR for an ADHD medication will be assigned to a pharmacist on the regional team. Pharmacists will review requests using a standard protocol. They will call parents via telephone to elicit additional information where needed, file ADHD medication prescriptions where appropriate, and send follow-up secure messages.

In the PCP Care group, each ADHD medication RAR will be sent to the PCP. Physicians will review requests using the standard regional protocol (as well as any existing medical center-level protocols). Following this protocol, physicians call patients via telephone to elicit additional information where needed, file ADHD medication refill prescriptions when appropriate, and send follow-up secure messages.

Due to system technical constraints, during this study it will not be possible to withhold RARs assigned to the Pharmacist Care group from the inboxes of the patients' PCPs. To ask physicians to not handle RARs assigned to the Pharmacist Care group, the regional director of desktop medicine sent an email to all pediatric chiefs at the start of the study period explaining the study and asking them to cascade the message to pediatricians to avoid handling RARs at the facilities selected for the Pharmacist Care group.

4.3. Randomization. Of the facilities in KPNC, 63 are eligible to be included. One facility (South Sacramento, which does not use this virtual care approach) will be excluded. The eligible facilities were assigned at random to either the Pharmacist Care or PCP Care arm. The goal of the randomization assignment plan was to balance on these variables:

- Number of estimated ADHD refill requests (based on ADHD med refill data)
- Race and ethnicity
- Sex
- Neighborhood deprivation index
- Age

We used covariate-constrained randomization, a method to prevent imbalances on important variables that may be associated with the outcomes.⁷ We conducted preliminary analyses to characterize facilities with regard to the above variables. We have chosen these variables for use in the restricted randomization given the expected association with study outcomes, along with the expected level of between facility variability which would increase the likelihood of between-arm imbalance.

Using these variables, we enumerated all possible outcomes of randomization and eliminated all allocations of the facilities to the two groups that do not meet specified between-group balance criteria. Standard diagnostics were applied in selecting the covariate balance criteria, ensuring no threats to the validity of the study design, including extreme reductions in total possible allocations for the trial, and instances of cluster pairs never/rarely or always/often randomized to the same arm. An allocation of facilities to the two arms for implementation was randomly selected from the set of allocations that meet the final covariate balance criteria.

The balance criteria were: maximum 5% between arm difference in total membership, 30% difference in total Black, 20% for each of White, Asian and Hispanic race/ethnic groups, and 0.25 standard deviation difference in mean NDI.

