We will also ask parents to indicate the mode by which they would prefer to make future ADHD medication refill requests, e.g. secure message or a telephone, video, or in-person appointment.

4.6. Statistical analysis plan.

The primary analysis will treat each patient as part of the group to which their facility was assigned (intention-to-treat). However, some patients in the Pharmacist Care group might have unintentional crossover and be handled by physicians instead of pharmacists. For this reason, we will conduct a secondary analysis in which patients are grouped based on the initial management approach they actually received (pharmacist or physician, based on which type of clinician first contacted the patient), similar to a per-protocol analysis. An RAR first accessed by a pharmacist and later accessed by physician will be counted in the pharmacist group.

The primary outcome is binary, i.e., whether or not a patient who had not had a weight check in the 6 months before the refill request is referred for an appropriate follow-up visit. This will be compared between study groups using mixed effects logistic regression providing point and interval estimates of outcome odds ratios associated with study group. This analysis technique accounts for the within-facility and within-patient correlation to obtain valid estimates of treatment effects and associated standard errors. The pre-specified set of covariates for inclusion in regression models include: study group and covariates used in the randomization procedure (i.e. patient socioeconomic status (using the Neighborhood Deprivation Index), patient age, sex, race and ethnicity, and comorbidity score). Study group and other covariates will be treated as fixed effects and facility will be handled as a random effect.

In addition, exploratory/sensitivity analyses will examine the impact of including additional covariates in our estimation of treatment effect, with focus on variables with chance imbalance in distributions by treatment group, as determined in preliminary analyses. Analyses resulting in

an appreciable change in the estimate of treatment differences or increased precision of the treatment effect will be noted.

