For the secondary outcomes, we will compare the days from the secure message request to prescription order or medication fill between the Pharmacist Care and PCP Care groups using linear mixed regression models, providing point and interval estimates of between-group differences in mean outcomes. If the numbers of days have a skewed distribution, log transformation will be used. Analyses of other continuous secondary outcomes will be similar. The approach to inclusion of covariates and sensitivity/exploratory analyses is as described for Aim 1.

For patient satisfaction, care experience scores will be compared between the study groups using linear mixed effects regression with log transformation if needed for skewed data, with analyses paralleling that described for the secondary outcomes. For analyses, categorical responses will be combined into a binary variable (Excellent or Very Good vs. Good, Fair, or Poor).

For all aims, secondary analyses will assess variation in the estimates of treatment effect by age, sex, socioeconomic status (using the Neighborhood Deprivation Index), and race and ethnicity, via stratification by level of the potential effect modifier. These stratified analyses will inform the fitting of mixed effects regression models with appropriate cross-product terms between the potential effect modifier and study group indicator variable, allowing for a more formal assessment of heterogeneity in treatment effect.

A facility may drop out before completion of the study if they were assigned to PCP Care but add local pharmacist management, thus diverging from their assigned group. ADHD medication refill requests to such a facility will be censored as of the dropout date (the date that local pharmacist management began).

Tests of significance will be two-tailed with an alpha of .05. No Bonferroni or other formal correction for multiple comparisons will be used, but results will be interpreted with the multiple testing issue in mind.

4.8. Sample size and power. To estimate the available sample, we extrapolated from data analyzed during the pilot period in April 2024.

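### Similar or comparable outcomes would count in favour of Pharmacist Care, but nothing ties those words to the planned intervals, so a non-significant difference could be read as support

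*Combined protocol and SAP*

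**What the plan says.** - **Abstract, Potential Conclusions and Relevance:** results count in favour of the programme if Pharmacist Care "has better or similar outcomes compared with PCP care, this will provide evidence supporting continuation of this approach". The word similar is not defined.
- **Abstract, Potential Results:** the hypotheses for Pharmacist Care are "higher quality of care, faster time to prescriptions and fills, and higher parent satisfaction".
- **Section 1, Aim 3** (labelled an example hypothesis): "Parents in the Pharmacist Care group will report comparable satisfaction with the process compared with the Physician Care group".
- **Section 4.6, testing:** "Tests of significance will be two-tailed with an alpha of .05".
- **Section 4.6, estimation:** the primary outcome is analysed by "mixed effects logistic regression providing point and interval estimates of outcome odds ratios associated with study group". The time outcomes use linear mixed models, "providing point and interval estimates of between-group differences in mean outcomes". For satisfaction, "care experience scores will be compared between the study groups using linear mixed effects regression", along the same lines as the other secondary outcomes. The same paragraph also collapses the responses into two categories.
- **Section 4.8 and Appendix A:** least detectable differences only. For the primary outcome, section 4.8 itself concedes good power for large differences only.

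No margin, equivalence or non-inferiority test, or confidence-limit criterion appears anywhere.

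**The concern.** Two statements in the plan depend on showing that the arms are alike: the similar half of the Abstract's conclusion, and Aim 3. A test of no difference cannot show that. The interval could inform it, but the plan does not say how the interval would be used. With the criterion left open, a p-value above .05 is an easy thing to report as similar, and a trial of this size may well produce one even if Pharmacist Care does worse.

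The findings are meant to inform whether the programme continues, how pharmacist effort is deployed, and the debate on the Ryan Haight extension. The primary outcome concerns children with no weight recorded in 6 months, and section 2 calls checking weight a key purpose of follow-up. Aims 1 and 2 are superiority hypotheses, which difference tests fit. The gap is confined to the words similar and comparable.

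**Working it through.** **Inputs from section 4.8 and Appendix A.** Primary outcome: N = 95, 63 clusters of 1.5. Aim 2: N = 315, clusters of 5. Survey: N = 189, clusters of 3. ICC .03, two-sided alpha .05, power 80%, PCP Care referral rate (P0) of 50% or 80%. **Assumed, because the documents give no threshold:** true deficits of 10, 15 and 20 points.

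**Step 1. Reproduce the plan's own figures.** Design effect = 1 + (m − 1) × ICC; effective n per arm = (N/2) / design effect.
- Primary: design effect 1 + 0.5 × .03 = 1.015; n = 47.5/1.015 = 46.8. The unpooled two-proportion formula gives 0.768 and 0.976; the pooled formula gives 0.775 and 0.979. Stated: 77% and 98%.
- Aim 2: design effect 1.12; (1.96 + 0.84) × √(4 × 1.12/315) = 0.334 SD. Stated: 0.334.
- Survey: design effect 1.06; (1.96 + 0.84) × √(4 × 1.06/189) = 0.42 SD. Appendix A has 0.42. The .037 in section 4.8 does not reproduce.

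The trial is therefore sized for two-sided differences.

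**Step 2. Expected interval width with no true difference.**
- Primary, P0 = 50%: 1.96 × √(2 × .50 × .50/46.8) = 0.203, about 20 points.
- Primary, P0 = 80%: 1.96 × √(2 × .80 × .20/46.8) = 0.162, about 16 points.
- Survey: 1.96 × √(4 × 1.06/189) = 1.96 × 0.150 = 0.29 SD.

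**Step 3. Chance of a non-significant result when Pharmacist Care is truly worse by d.** Normal approximation with P1 = P0 − d and SE = √{[P0(1 − P0) + P1(1 − P1)]/46.8}. The chance is Φ(1.96 − d/SE) − Φ(−1.96 − d/SE). For d = 15 points from 50%: SE = √[(.2500 + .2275)/46.8] = 0.101; d/SE = 1.485; Φ(0.475) = 0.68, and the second term is negligible.

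| True deficit (assumed) | P0 = 50% | P0 = 80% |
|---|---|---|
| 10 points | 84% | 80% |
| 15 points | 68% | 62% |
| 20 points | 48% | 42% |

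A pooled standard error in the test changes these by at most about 2 points (69%/63% at 15 points; 49%/44% at 20).

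For the survey mean score, an assumed deficit of 0.2 SD is non-significant 73% of the time, and 0.3 SD 48% of the time.

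**Step 4. Sensitivity to N.** The Aim 3 paragraph of section 4.8 speaks of 315 parents in each group, but then of 189 completed surveys across groups. If 315 is per arm, the primary analysis has about 630 × 0.30 = 189, say 190 children (clusters of 3, design effect 1.06, 95/1.06 = 89.6 per arm). The half-widths become 1.96 × √(.50/89.6) = 15 points and 1.96 × √(.32/89.6) = 12 points. A 15-point deficit is then non-significant about 46% or 37% of the time.

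**The case against.** **No formal decision rule exists.** The sentence on better or similar outcomes is an abstract-level statement about potential conclusions, and Aim 3 is an example hypothesis for a secondary outcome. Section 4.6 never says that a non-significant result will be read as similarity. This stands. A reader might infer that the plan commits to that misreading, but it only leaves room for it.

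**Intervals are already planned.** This also stands. A reader might infer that similar can only mean not significant, and the documents do not support that, because similarity could be judged from the intervals. What is missing is any statement that it will be.

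**The power limit is disclosed.** True for the primary outcome in section 4.8. The disclosure does not say what a null result may be used to claim.

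**The percentages count p > .05, not claims of similarity.** Correct. With a true 15-point deficit and N = 95, the chance that the point estimate is better than −5 points is 1 − Φ(.10/.101) = 16% from 50%, or 1 − Φ(.10/.091) = 14% from 80%. Most non-significant results would still show a visible deficit. The 62% to 68% is therefore not the chance of a false claim of similarity. It shows how little non-significance alone excludes.

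**N = 95 is insecure.** It extrapolates pilot counts of free-text secure messages, while section 4.1 moves the study to structured refill requests without giving their volume. The percentages would change with N; the missing criterion would not.

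**Similar outcomes may be a legitimate reason to continue.** Section 2 says pharmacists took over adult requests to help busy physicians. That is a good reason not to delete the word similar.

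**Conclusion.** The concern holds in a limited form. The plan gives weight to similar and comparable outcomes, tests and sizes only for differences, and does not connect those words to the intervals it will report. At N = 95 and ICC .03, a null primary result would typically leave differences of about 16 to 20 points unexcluded; for the survey, about 0.29 SD. The chance that a real deficit goes undetected rests on assumed deficits and an uncertain N: for 15 points it runs from 68%/62% at N = 95 to 46%/37% at about 190.

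The planned difference tests remain suitable for Aims 1 and 2. The documents do not show which of higher and comparable was the satisfaction hypothesis; they only show that the two conflict. Severity is minor to moderate: no estimate changes, only what may be concluded from it.

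**What to change.** 1. State in section 4.6 that a non-significant difference will not be described as similar or comparable.
2. For each aim, report the 95% CI for the between-group difference (for the primary outcome, a risk difference alongside the odds ratio) and the largest disadvantage to Pharmacist Care that the interval does not exclude. Base any statement of similarity, including the one in the Abstract, on that limit.
3. Reconcile the Abstract (higher satisfaction) with Aim 3 (comparable). The sponsor should say which was the hypothesis. This version is dated August 27, 2024, after the June 21, 2024 end of the study period in section 4.1, so a reviewer should not pick one now.

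None of this needs a margin, new data or a larger sample. The added work is a few sentences and a risk-difference estimate from the primary model. The price is that a null result supports a narrower conclusion: that disadvantages beyond the stated limit are excluded, and no more.

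### The only dated cohort rule in the body of the protocol cannot describe the PCP Care arm, names the wrong request type, and covers 7 weeks where the Abstract and sample size use 9

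*Combined protocol and SAP*

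**What the plan says.** **Entry rule and dates.** Section 4.1 states: "The formal study period will include patients with secure messages sent to the regional pharmacy team from May 6, 2024 to June 21, 2024", and gives the length as 7 weeks. The Abstract describes parents "who request ADHD medication refills via secure messages from April 29 to June 28, 2024". Section 4.8 and Appendix A assume 9 weeks at 35 requests per week, giving 315.

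**Request type.** Section 4.1 explains that free-text secure messages were hard to identify in the pilot and differ from RARs, so "this study was designed to focus only on RARs".

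**Routing.** Section 4.2 says that in the Pharmacist Care group "each RAR for an ADHD medication will be assigned to a pharmacist on the regional team". For the other arm it says: "In the PCP Care group, each ADHD medication RAR will be sent to the PCP". It adds that, for technical reasons, Pharmacist Care RARs cannot be kept out of PCP inboxes.

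**Recipient.** Section 1 and the opening sentence of 4.1 cover requests to pediatricians and family medicine physicians. The target-population sentence later in 4.1 mentions only the child's pediatrician.

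**Analysis.** Section 4.6 specifies intention-to-treat by the facility's assignment and expects that physicians will handle some Pharmacist Care patients. It adds a secondary analysis by the type of clinician who made first contact.

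**The concern.** A cluster trial needs one rule that decides, in the same way in both arms, which requests enter the dataset. The only dated rule in the body selects on routing to the pharmacy team. Routing happens after randomisation and differs by design between the arms. An analyst who follows it literally has no PCP Care arm and must devise a second rule for those facilities.

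If the Pharmacist Care arm were then taken from the pharmacy queue and the PCP Care arm from an EHR query, the arms would be sampled differently. A Pharmacist Care RAR dealt with by a physician could be missing from the first source, with no counterpart in the second. Intention-to-treat governs how admitted requests are grouped. It does not say which requests are admitted.

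The two windows leave two weeks of requests (April 29 to May 5 and June 22 to June 28) that could be in or out. The recipient wording leaves family medicine requests in a similar position. That matters for crossover too, since the emails described in 4.1 and 4.2 asking clinicians to leave Pharmacist Care RARs alone went to pediatric departments and chiefs.

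**Working it through.** **1. Entry rule against each arm**

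| Element of the 4.1 sentence | Pharmacist Care | PCP Care |
|---|---|---|
| Sent to the regional pharmacy team | Consistent with 4.2 | Not met: 4.2 sends the RAR to the PCP |
| Secure message | Conflicts with the RAR-only scope in 4.1 | Same conflict |

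The target-population sentence in 4.1 is neutral between arms and refers to RARs, but it has no dates and no method of identification. No section gives a rule that is both dated and neutral between arms.

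**2. Calendar**

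- May 6 to June 21, 2024: Monday to Friday, 47 days, 35 weekdays, so 7 working weeks. The length stated in 4.1 is right for its dates.
- April 29 to June 28, 2024: Monday to Friday, 61 days, 45 weekdays, so 9 working weeks. This is the period used in 4.8 and Appendix A.

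**3. Sample size and detectable effects**

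Inputs from 4.8 and Appendix A: 35 requests per week, 63 clusters, 30% without a recent weight, 60% survey response, ICC 0.03, power 80%, two-sided alpha 0.05. Assumed here: equal arms and a normal approximation.

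- Requests: N = 35 × weeks. 35 × 9 = 315 (the plan's figure); 35 × 7 = 245, which is 70/315 = 22% fewer.
- Primary-outcome patients: 0.30 × 315 = 94.5 (plan: 95); 0.30 × 245 = 73.5, about 74.
- Design effect: DE = 1 + (m − 1) × 0.03, with m = n/63.
- Means: detectable effect = (1.960 + 0.842) × √(4 × DE / n).
  - 9 weeks: m = 5, DE = 1.12, 2.802 × √(4.48/315) = 0.334 (the plan's figure).
  - 7 weeks: m = 3.89, DE = 1.087, 2.802 × √(4.347/245) = 0.373.
- Proportions, unpooled variance: solve (p − p0)² = 2.802² × [p(1 − p) + p0(1 − p0)] / n_eff, with n_eff = (n/2)/DE.
  - 9 weeks: n_eff = 47.25/1.015 = 46.6.
  - 7 weeks: n_eff = 36.75/1.005 = 36.6.

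| Quantity | Plan states | 9 weeks, recomputed | 7 weeks |
|---|---|---|---|
| Requests | 315 | 315 | 245 |
| Primary-outcome patients | 95 | 94.5 | 73.5 |
| Aim 1, detectable against 50% | 77% | 76.9% (pooled 77.6%) | 79.7% (pooled 80.7%) |
| Aim 1, detectable against 80% | 98% | 97.6% (pooled 98.0%) | 99.1% (pooled 99.5%) |
| Aim 2, SD units | 0.334 | 0.334 | 0.373 |
| Survey, SD units (Appendix A) | 0.42 | 0.420 (n = 189) | 0.471 (n = 147) |

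The plan's figures reproduce at 9 weeks. The 7-week column is illustrative: 35 per week is a pilot rate for secure messages, and the documents give no RAR rate.

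**4. Form of any selection bias**

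If a share x of Pharmacist Care RARs were omitted, and their referral rate differed from that of the retained RARs by d, the arm's observed rate would be off by −x × d. The documents give neither x nor d. Taking x = 10%, 20% or 30% and d = +20 points purely as assumptions, the arm would be understated by 2, 4 or 6 points. With d = −20 points it would be overstated by the same amounts.

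**The case against.** The strongest reply is that the intent is clear and the sentence is leftover pilot wording. It mainly sets the period. The next sentence makes the RAR the unit of analysis, and 4.6 plainly analyses both arms. The plan uses secure message loosely elsewhere, including in the secondary outcomes in 4.4.1 that apply to both arms. All of this is fair. It answers a reader who might infer that free-text messages were meant to be the cohort, or that no PCP Care arm was planned. It does not supply a dated rule for selecting that arm.

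A reader might also infer that physician-handled RARs are lost from the Pharmacist Care arm and that intention-to-treat is already broken. The documents do not support this. Section 4.2 assigns every Pharmacist Care RAR to a pharmacist, and a copy in a PCP inbox does not imply removal from the pharmacy queue. Section 4.6 keeps crossovers in their assigned group, and its analysis by first contact needs those RARs in the data. Section 4.5 names EHR data and access logs as sources. The pool handlers who forward straightforward requests in 4.8 belong to the pilot's secure-message process, so they say little about RARs. What remains is a risk that the wording permits.

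Nor does 4.1 simply exclude family medicine: its opening sentence includes it, so the inconsistency lies within the section.

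**Conclusion.** The entry rule is wrong as written and should be corrected. Three parts follow from the text without assumptions: the rule cannot describe the PCP Care arm, it names a request type that the study set aside, and its 7-week window disagrees with the Abstract and with the 9 weeks behind the 315. The recipient wording in 4.1 also needs to be made consistent.

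One-sided omission of physician-handled RARs is possible and not documented. Its size and direction are unknown, so no figure for bias in the referral rate should be attached to it. In particular, a claim that the Pharmacist Care rate would be understated needs a direction that the documents do not give.

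On size, 245 requests and about 74 primary-outcome patients should not be read as a forecast or as proof that the trial is smaller than planned. They rest on the pilot rate of 35 per week. Section 4.1 says that the flow of identifiable secure messages was too low for the intended sample, which is why the study moved to RARs. The figures show only what the window conflict means at the plan's own rate: 22% fewer requests, a detectable Aim 2 effect of about 0.373 SD in place of 0.334, and an Aim 1 contrast of 50% against about 80–81% in place of 77%.

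**What to change.** Replace the sentence in 4.1 with one rule for both arms. Suggested text: *The cohort comprises all ADHD medication RARs for patients younger than 18 years received from [start date] to [end date] at any of the 63 randomised facilities and addressed to a pediatrician or family medicine physician. RARs are identified by the same EHR query in both arms, regardless of routing or of who handled them.*

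Then:

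- The sponsor confirms which window applied and uses it in the Abstract, 4.1, 4.8 and Appendix A. The document is dated August 27, 2024, after both windows closed, so this should be a matter of record.
- If the window is 7 weeks, restate the sample size and detectable effects, preferably with an RAR rate.
- Align the target-population sentence in 4.1 with the opening of 4.1 and section 1 on family medicine, or state the narrower scope in all three places.
- Use RAR in place of secure message where an RAR is meant.

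The cost is one replaced sentence, a few aligned dates and terms and, if the window is 7 weeks, a short recalculation. No new data collection is needed.
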